## REST: Reducing the Experience of Menopausal Symptoms through Temperature

questionnaires, and sent home with a 2-week diary to confirm their eligibility with respect to number of hot flashes/night sweats. If it is not possible for the participant to come to one of these locations, the baseline questionnaire and consent will be sent to the participant to be completed at home and mailed back. Two copies of the consent form will be sent to the participant. After received, a study team member will speak with the participant to present the elements of consent, the content of the study, and answer any questions. At the end of the discussion, the participant will be advised to sign and date one form and return it. The second form should be kept by the participant for documentation. Upon receipt of the signed form, the study team member will sign and date with the current date, and add a note detailing the date discrepancy.

We will ask participants to keep a record of their hot flashes throughout the day by either using a counter app on their phone or maintaining a paper log. After two weeks, women will mail in their diaries and continue to record their daily hot flashes until they are notified by study staff of their eligibility, within a week of receiving the diary.

If still eligible based on the 2-week diary, participants will return to the PHS Research Center to receive a cooling mattress pad and container of distilled water (used to fill cooling mattress pad) to take home and use for the next 9 weeks. If it is not possible for the participant to return to the Research Center, the Chilipad will be delivered to the participant at a mutually agreed upon location. We will allow one week for women to determine the optimal temperature of the cooling mattress pad and the next 8 weeks for the data collection of hot flashes/night sweats while using the cooling mattress pad. Some participants may be away from home and unable to use the cooling mattress pad while participating in the study. We will ask that participants indicate on the Hot Flash Diary whether or not they used the cooling mattress pad the prior night and continue tracking their hot flashes/night sweats even if they did not use the mattress pad.

Participants will mail in their completed Hot Flash Diary every two weeks in a pre-stamped and pre-addressed envelope to ensure that data is being consistently recorded.

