## **Statistical Considerations**

### **Analytical Plan**

Our primary outcomes of interest will be change in number of daily hot flashes (total, daytime, and nighttime) over the eight week period. We will model our outcome in both absolute terms (average number of daily hot flashes each week) as well as in terms of percentage change in average daily hot flashes measured from baseline. We will first conduct a simple t-test on the difference in average number of daily hot flashes at baseline and eight weeks to see if this average difference is significantly different from the null value of zero. We will also conduct repeated measures models with time included as ordinal week (0-9) and the dependent variable pertaining to average daily number of hot flashes for each week or percent change in average daily number of hot flashes for each week. In the simplest repeated measures models we will examine whether the parameter estimate for week is significantly different from zero. We will also examine the effects of covariates such as age and menopause status to determine which are significantly associated with the outcomes, and to estimate an adjusted (least squares mean) outcome measure that will serve as an accurate comparison to our historical control (see below).

Secondarily, we will model the continuous outcome of the total PSQI sleep score, as well as the subscores, using a similar repeated measures approach to that described above

In addition to examining, within our sample of cooling mattress pad users, the question of whether symptoms (hot flashes, sleep disturbance) improve over time, we will also compare any observed improvements with those found in our control group from the Acupuncture in Menopause (AIM) Study to see if cooling mattress pad users experienced significantly different levels of change over time compared to an historical control. (We note that in our AIM control group, there was on average an approximately -3.3% decline in average number of daily hot flashes from baseline to week 8, and there was an increase of .49 in total score on the PSQI over the same period.)

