### Sample Size

This is a single site, single arm pilot study designed to obtain preliminary evidence that the cooling mattress pad can help reduce hot flashes and night sweats. We will compare results to historical controls from a previous study. Based on this previous study, we estimate that women recruited to our sample will be experiencing, on average, approximately 10 hot flashes at baseline. The average decline in number of daily hot flashes over an 8 week period in the control arm of this study was 0.36 (standard deviation 2.85). In comparison to the 0.36 fewer hot flashes on average in the absence of intervention (i.e., null hypothesis), we will be able to detect in our sample of 24 a decline of 2.1 in absolute number of average daily hot flashes from baseline to week 9, with 80% power and a two-tailed alpha of 0.05. We note that the ‘detectable’ anticipated decline of 2.1 in number of hot flashes (or just over 20% decline from baseline) is a conservative estimate; in our previously-sited study, a 35% decline in number of hot flashes over 8 weeks has been observed.

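### The only named t-test is against zero, but the sample size is powered against a 0.36/day decline, and the historical-control comparison that addresses that null has no named test or priority

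*Combined protocol and SAP*

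**What the plan says.** The Analytical Plan begins with a t-test whose subject is the "difference in average number of daily hot flashes at baseline and eight weeks". The stated purpose of this test is "to see if this average difference is significantly different from the null value of zero". For the simplest repeated measures models, "we will examine whether the parameter estimate for week is significantly different from zero". Both therefore use a null of no change.

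The Sample Size section sets a different null: "In comparison to the 0.36 fewer hot flashes on average in the absence of intervention (i.e., null hypothesis". Against it, 24 women are said to be enough to detect a decline of 2.1 per day "from baseline to week 9, with 80% power and a two-tailed alpha of 0.05".

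The Analytical Plan also looks to the AIM control group. It will use covariates "to estimate an adjusted (least squares mean) outcome measure that will serve as an accurate comparison to our historical control", and it asks whether pad users show "significantly different levels of change over time compared to an historical control". This comes after the within-sample analyses, as an addition to them. No test is named. The plan does not say whether 0.36 is a fixed benchmark or AIM individual data will be used, nor which result supports an efficacy conclusion.

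**The concern.** The power statement should describe the test on which the conclusion rests. Here the power belongs to one null and the only named test to another. In a single-arm study, a test against zero shows whether symptoms changed. It cannot separate an effect of the pad from the decline that occurs without it, which is presumably why the AIM control group was brought in.

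The two nulls can give different answers on the same data. If a decline is significant against zero but not against 0.36 (or against AIM), the plan has no rule for which result counts as preliminary evidence of efficacy, and the choice could be made after the data are seen.

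The endpoint wording also differs: eight weeks in the Analytical Plan, week 9 in the Sample Size section. The Design section allows one week for finding a temperature and then "the next 8 weeks for the data collection of hot flashes/night sweats while using the cooling mattress pad", so these may be the same point, but the plan does not say so.

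**Working it through.** **Inputs (Sample Size section).** n = 24; SD of change 2.85; null decline 0.36; target decline 2.1; two-sided alpha 0.05. The section equates 2.1 with a little over a fifth of a baseline of about 10, so 2.1 is the total decline and the excess over the null is 2.1 − 0.36 = 1.74.

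**Common quantities.** SE = 2.85/√24 = 0.5818; t(0.975, 23 df) = 2.069. Power is from the noncentral t with 23 df and noncentrality (true decline − null)/SE.

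**1. The plan's figure, null fixed at 0.36.** Noncentrality 1.74/0.5818 = 2.99; power 81.7%. With n = 23 it is 79.9%, so 24 is the smallest n that reaches 80%. The decline detectable at 80% is 0.36 + 1.70 = 2.06, which rounds to 2.1. The arithmetic is sound: it is a one-sample t-test that treats 0.36 as known.

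**2. The named test, null zero.** Noncentrality 2.1/0.5818 = 3.61; power 93.3%. The decline detectable at 80% is 1.70, and 17 women would suffice (n = 16 gives 78.7%, n = 17 gives 81.4%).

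**3. Where the two disagree.** Critical observed decline against zero: 2.069 × 0.5818 = 1.20. Against a fixed 0.36: 0.36 + 1.20 = 1.56. Between these, the named test is significant and the plan's null stands.

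| True decline/day | Significant vs zero but not vs fixed 0.36 |
|---|---|
| 0.36 | 6.1% |
| 1.0 | 19.5% |
| 2.1 | 11.6% |
| 3.5 | 0.06% |

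If the true decline is only the background 0.36, the zero-null test shows a significant decline 8.6% of the time, against a nominal 2.5% in that direction.

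**4. A two-sample comparison with AIM.** The control size is not in the documents, so a range is assumed, with SD 2.85 in both groups and a pooled t-test: SE = 2.85 × √(1/24 + 1/n_c). For n_c = 40, SE = 0.736, t = 1.999, and the critical decline with AIM at 0.36 is 0.36 + 1.999 × 0.736 = 1.83.

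| Assumed AIM controls | Power at 2.1 | Detectable decline (80%) | Critical observed decline |
|---|---|---|---|
| 24 | 54% | 2.71 | 2.02 |
| 40 | 64% | 2.45 | 1.83 |
| 100 | 76% | 2.19 | 1.64 |
| 200 | 80% | 2.09 | 1.57 |

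The detectable decline rounds to 2.1 only with 126 or more controls, and power at exactly 2.1 reaches 80% with 186. If the AIM mean is held at its observed 0.36, the powers are 56%, 68%, 78% and 82% (simulated). At a true decline of 2.1, the chance of being significant against zero but not against AIM is 29%, 18% and 13% with 40, 100 and 200 controls (simulated).

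**5. A one-sample test against a fixed 0.36.** This ignores sampling error in the AIM mean. With no true difference, the variance of the contrast is larger by a factor 1 + 24/n_c, so the two-sided error rate is P(|t₂₃| > 2.069/√(1 + 24/n_c)): 11.6%, 7.6% and 6.3% with 40, 100 and 200 controls.

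**6. Dropout.** No allowance is stated. With 20 completers, power against a fixed 0.36 is 73.6%; against AIM it is about 50%, 59%, 70% and 74% with 24, 40, 100 and 200 controls.

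**The case against.** The strongest reply is that the comparison matching the Sample Size null is already planned. The Design, Analytical Plan and Sample Size sections all commit to a historical control, and the Analytical Plan separates improvement over time from the comparison with AIM. On that reading the zero-null test answers whether women improved, the AIM comparison is the powered one, and only wording is missing. That is largely fair about intent. It does not supply the test, the treatment of AIM sampling error, or the priority, and the stated power fits a two-sample test only if the AIM control group is large.

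It is also true that this is a pilot seeking preliminary evidence, that the zero-null test is not underpowered, and that a large effect makes the issue small: at a decline of 3.5/day the disagreement in step 3 almost vanishes. But the 35% decline cited in the Sample Size section comes from the AIM study and not from the pad, and the plan's own design value is 2.1.

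Two limits stand. The two-sample figures rest on assumed control sizes and an unadjusted test with equal SDs, and the planned adjusted repeated measures estimate may be more or less precise. And a p-value against non-concurrent controls does not remove differences between the samples, so naming that test does not make the evidence firm.

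**Conclusion.** The concern holds and should be fixed. The stated 80% power belongs to a one-sample test against a known 0.36, which the Analytical Plan does not name. The test it does name has 93.3% power at the same decline. The plan leaves open which null decides efficacy, and observed declines between about 1.20 and 1.56/day would pass one and fail the other. These figures use only the documents' inputs and normally distributed changes. The power of an actual comparison with AIM cannot be fixed from the documents.

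The zero-null test is valid as a test of change; the fault arises if it is read as efficacy. The week 8 and week 9 wording and the absent dropout allowance are minor side points.

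**What to change.** In the Analytical Plan, state that the efficacy conclusion on total daily hot flashes rests on the planned comparison with the AIM controls. Name a test that allows for sampling error in the AIM estimate, for example a two-sample t-test on change, or a group term in the repeated measures model if AIM individual data are used. Report the change from zero with its 95% CI as descriptive. The documents give no AIM figure for daytime or nighttime counts, so report those with CIs unless AIM values are added.

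In the Sample Size section, give the AIM control size and restate the power for the named comparison. If a one-sample test against a fixed 0.36 is kept instead, say that it treats 0.36 as known and that its true error rate exceeds 5%. Use one endpoint week in both sections.

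The cost is wording in two sections, one figure from the AIM study and one recalculation, with no added patients. The downside is a higher bar than the zero null's 1.20/day and possibly a stated power below 80%, both depending on the AIM control size as tabulated in step 4. The change should be made before results are known.

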### Covariates

In addition to sociodemographics (Appendix I) (age, education, marital status, employment status), the following covariates will be assessed:

- **Symptom Sensitivity** is a measure of symptom sensitivity or amplification. The Somatosensory Amplification Scale (SSAS) is a 10-item questionnaire that assesses sensitivity to a range of uncomfortable bodily sensations and physiologic states which are not typically symptoms of disease. The SSAS has been shown to prospectively predict persistence of hypochondriacal symptomatology in transient hypochondriacal patients. This measure has been shown to be a strong predictor of vasomotor symptom reporting. It is included as a covariate because it is highly related to symptom reporting and symptom sensitivity may be an important variable related to treatment efficacy (Appendix J).
- **Health history and current medications.** At the baseline visit, participants will be asked to bring in all medications, vitamins, and herbal supplements they are currently taking so that these can be recorded (Appendix K). Medications will again be assessed at follow-up (Appendix O).
- **Health behaviors** will include standard questions on smoking and physical activity. Active *smoking* will be ascertained from the American Thoracic Society questions, *Physical activity* will be measured using 3 items we have used in previous studies (Appendix L). Change in health behaviors will be assessed (Appendix N)

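### The adjusted mean for the AIM comparison appears to rest on covariates screened for significance in 24 women; fix a short baseline set in advance instead

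*Combined protocol and SAP*

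**What the plan says.** The Analytical Plan (combined protocol and SAP, Statistical Considerations) states: "We will also examine the effects of covariates such as age and menopause status to determine which are significantly associated with the outcomes". The sentence then adds a second purpose, "to estimate an adjusted (least squares mean) outcome measure that will serve as an accurate comparison to our historical control". Later in that section the team undertakes to "compare any observed improvements with those found in our control group from the Acupuncture in Menopause (AIM) Study" and to see whether change over time differs significantly between the two.

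The list of candidates is open. The Analytical Plan names age and menopause status only as examples. The Covariates section adds education, marital status and employment status, and says that "the following covariates will be assessed": symptom sensitivity (SSAS), health history and medications, smoking and physical activity. That makes about nine. SSAS is the only one given a prior reason for inclusion. Baseline hot flash frequency is not named in either section. Change in health behaviors and the medication update also appear under Covariates, and the Measures Timeline places both at follow-up only.

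No section gives an entry threshold, a retention rule, a fixed adjustment set, or the covariate values at which the adjusted mean is evaluated.

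**The concern.** REST has a single arm, so nothing in the design balances its women against the AIM controls. Covariate adjustment is the only protection that the plan describes for that comparison. A covariate biases the comparison when it predicts the change and also differs between the two studies. Significance among the 24 pad users bears on the first condition, with little power, and says nothing about the second.

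If retention depends on that test, a real confounder can be dropped because the sample is small, and an unrelated variable can be kept by chance. The slope of a kept predictor also tends to be overstated. If retention does not depend on the test, the adjustment set is still open to choice after the data have been seen.

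**Working it through.** **Inputs from the Sample Size section.** n = 24, null decline 0.36, SD of change 2.85, two-sided alpha 0.05, power 80%. **Assumed, because the documents do not give them:** entry at p < 0.05, the covariate-outcome correlation r, the REST-AIM difference in the covariate in SD units, independent null covariates, and one change score per woman. A repeated measures model could have somewhat different power.

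**1. The plan's own figure.** The plan says "we will be able to detect in our sample of 24 a decline of 2.1 in absolute number of average daily hot flashes", "with 80% power and a two-tailed alpha of 0.05". SE = 2.85/√24 = 0.582. A one-sample t-test against a fixed 0.36 (noncentral t, 23 df) has 80% power at a difference of 1.70. The detectable decline is therefore 1.70 + 0.36 = 2.06, which rounds to the stated 2.1. At 2.1 − 0.36 = 1.74, power is 81.7%. The figure reproduces, and no covariate enters it.

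**2. Size of correlation needed.** With 22 df the critical t is 2.074. The smallest |r| giving p < 0.05 is 2.074/√(22 + 2.074²) = 0.404.

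**3. Chance that a real predictor is kept.** By Fisher's z, power ≈ Φ(atanh(r)·√21 − 1.96). For r = 0.3 this is Φ(0.3095 × 4.583 − 1.96) = Φ(−0.54) = 29%.

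| True r | Fisher z | Noncentral t | Simulation |
|---|---|---|---|
| 0.3 | 29% | 31% | 30% |
| 0.4 | 49% | 53% | 51% |
| 0.5 | 71% | 77% | 73% |

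A correlation of about 0.55 is needed for 80%. A binary covariate, such as menopause status, that shifts the change by 1.0, 1.5 or 2.0 hot flashes per day is kept 13%, 23% or 38% of the time with a 12:12 split, and 11%, 19% or 30% with 18:6.

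**4. Chance of a false predictor.** With nine independent null candidates, 1 − 0.95⁹ = 37%. The range is 23% for five and 40% for ten.

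**5. Bias left in the comparison.** The set-up has one confounder and no pad effect. The slope is estimated in REST only, and the adjusted mean is evaluated at the AIM covariate mean (100,000 simulated trials per setting). Unadjusted bias is r × 2.85 × shift. Screened bias is that value × (1 − proportion kept × mean slope inflation when kept). The inflation is about 1.72, 1.35 and 1.16 for r = 0.3, 0.4 and 0.5. Example with r = 0.3 and shift 0.5: 0.3 × 2.85 × 0.5 = 0.43, and 0.43 × (1 − 0.30 × 1.73) = 0.21.

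| r | Shift (SD) | Unadjusted | Screened | Always kept |
|---|---|---|---|---|
| 0.3 | 0.3 | 0.26 | 0.13 | 0.00 |
| 0.3 | 0.5 | 0.43 | 0.21 | 0.00 |
| 0.3 | 0.8 | 0.68 | 0.33 | 0.00 |
| 0.4 | 0.3 | 0.34 | 0.10 | 0.00 |
| 0.4 | 0.5 | 0.57 | 0.18 | 0.00 |
| 0.4 | 0.8 | 0.91 | 0.29 | 0.00 |
| 0.5 | 0.3 | 0.43 | 0.07 | 0.00 |
| 0.5 | 0.5 | 0.71 | 0.11 | 0.00 |
| 0.5 | 0.8 | 1.14 | 0.18 | 0.00 |

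Units are hot flashes per day. The sign follows the direction of the imbalance, so the bias could favour or disfavour the pad.

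**The case against.** The plan does not say that non-significant covariates are dropped. Its sentence gives two purposes joined by a plain conjunction, and SSAS is included on prior grounds, not by a screen. This stands, so the selection rule is an inference. It does not rescue the plan: significance is the only criterion mentioned, SSAS is not said to be retained whatever its p-value, and the adjustment set stays open on either reading.

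The size of the problem rests on assumptions. That also stands. The documents give neither AIM's covariate values nor any evidence of imbalance, and a covariate unrelated to the outcome causes no bias however much it differs. The residual bias is also modest against the planned detectable excess: 0.07/1.74 = 4% to 0.33/1.74 = 19%. Against the AIM decline of 0.36 it looks larger.

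A reader might infer that real confounders are usually left unadjusted, or that screening removes the protection altogether. The figures do not support this. At r = 0.4 retention is about even, at 0.5 the covariate is usually kept, and in every setting above screening removes at least half of the unadjusted bias.

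A reader might infer larger harm from a joint REST-AIM regression. With an assumed 50 AIM controls and eight noise covariates, that simulation gave bias of 0.18 to 0.46 and 8% to 15% false rejections. The plan does not describe that model, so the point does not rest on it.

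A reader might infer that post-treatment behaviour change will be adjusted for. It is listed under Covariates, but no section says that it enters the adjusted mean. Nor is baseline frequency ruled out: the list is open, week 0 is in the repeated measures model, and percent change from baseline is modelled.

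Finally, this is a pilot, and the t-test against zero and the simplest week model use no covariates. That limits the reach of the point to the AIM comparison. The plan nevertheless intends a significance statement there and expects the adjusted mean to be accurate.

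**Conclusion.** The concern holds in a limited form. The plan ties the adjusted mean for the AIM comparison to covariates examined for significance in 24 women and fixes no adjustment set. If the natural reading is right, moderate predictors are kept unreliably, and there is a 37% chance, not a certainty, of at least one false predictor among nine independent null candidates. For r of 0.3 to 0.5 and study differences of 0.3 to 0.8 SD, confounding is reduced but not removed, and a fixed adjustment does better at little cost. These bias figures depend on the assumed correlations, imbalance and 5% threshold, on a REST-only slope, and on evaluation at the AIM mean. The documents do not show that such an imbalance exists. The sample-size calculation and the unadjusted within-group analyses are not affected.

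**What to change.** In the Analytical Plan, replace selection by significance with a short set of baseline covariates fixed in advance on prognostic grounds. Baseline hot flash frequency, age and menopause status are examples, with SSAS added if AIM recorded it. Limit the set to variables confirmed as recorded in AIM, and keep all of them whatever their p-values.

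State that the adjusted mean is evaluated at the AIM covariate means. If AIM participant data are available, model both studies together with a study term instead. Where baseline frequency is an adjuster, use change or the post-baseline weeks as the outcome, so that week 0 is not on both sides of the model.

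State that the follow-up measures (change in health behaviors, updated medications) are not adjusters, since they are recorded after pad use and adjusting for them could remove part of any effect. Label other covariate associations as exploratory.

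The cost is SAP wording, a few degrees of freedom at n = 24, and a check of which variables AIM recorded. The documents do not list AIM's variables, so that check must come first.

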### **Inclusion Criteria**

- Women aged 45-60
- Peri or postmenopausal women (No periods for at least 3 months)
- Experiencing at least 4 hot flashes per day on average per week

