At the end of the 9 weeks, women will return to the Research Center or Center for Integrative Medicine, complete additional questionnaires and receive compensation for participating in the study. Participants may also complete the follow-up questionnaires by telephone or mail. Analyses will assess frequency of hot flashes/night sweats experienced by women before and after using the cooling mattress pad. We will use an historical control group to compare results from this study to a control group from a previous study.

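### The adjusted least squares mean offered as the comparison with the AIM controls is not, as described, adjusted to AIM's case mix

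*Combined protocol and SAP*

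**What the plan says.** The Analytical Plan describes repeated measures models with ordinal week (0-9) and, as outcome, "the dependent variable pertaining to average daily number of hot flashes for each week or percent change in average daily number of hot flashes". Covariates such as age and menopause status are examined "to determine which are significantly associated with the outcomes". The second purpose given for these covariate models is "to estimate an adjusted (least squares mean) outcome measure that will serve as an accurate comparison to our historical control (see below".

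For sleep, "we will model the continuous outcome of the total PSQI sleep score, as well as the subscores, using a similar repeated measures approach". A later paragraph separates the question of change within the pad users from a second step, which is to "compare any observed improvements with those found in our control group from the Acupuncture in Menopause (AIM) Study". The Design section says the same in general terms: "We will use an historical control group to compare results from this study to a control group from a previous study".

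AIM enters only through summary changes: about -3.3% in hot flashes and +0.49 in PSQI total score (Analytical Plan), and a mean decline of 0.36 per day with SD 2.85 (Sample Size). The Covariates section lists what REST will collect. It gives no AIM values and does not name baseline hot-flash frequency or baseline PSQI as a covariate.

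**The concern.** REST has one arm, and AIM is its only external comparator. Eligibility leaves the menopausal mix open ("Peri or postmenopausal women (No periods for at least 3 months"), so the REST and AIM samples may differ in composition. The least squares mean is the only device in the plan for dealing with that.

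A least squares mean is adjusted only to the covariate values at which it is evaluated, and only if the covariates enter the model in a way that affects the quantity being compared. The AIM figures are changes from baseline. If the REST model holds covariates as main effects on weekly counts, they shift the level at every week and not the change. A reader told that the measure is adjusted and accurate would take the difference from AIM as corrected for case mix when the described step does not correct it. The same applies to the PSQI, which follows the same approach.

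**Working it through.** **1. The plan's own figure.** Sample Size gives n = 24, SD 2.85, a null decline of 0.36, a detectable decline of 2.1, 80% power and two-sided alpha 0.05.
- Difference to detect: 2.1 - 0.36 = 1.74.
- Noncentrality of a one-sample t-test: 1.74 / 2.85 x sqrt(24) = 2.99, which gives 81.7% power.
- At exactly 80% power the detectable difference is 1.70, a decline of 0.36 + 1.70 = 2.06, or 2.1 rounded.

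The figure reproduces with AIM as a fixed constant. It does not use the least squares mean.

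**2. Weekly counts.** Write the additive model as y(i,w) = m(w) + b'x(i) + woman effect + error.
- Least squares mean at reference values x*: m(w) + b'x*.
- Change from baseline to week 8: [m(8) + b'x*] - [m(0) + b'x*] = m(8) - m(0).

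The covariates cancel whatever x* is, AIM's values included. With complete data and week as categories, the estimate of m(8) - m(0) is the raw REST change. With linear week it is 8 times the unadjusted slope.

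**3. Percent change.** Here the outcome is already a change, so b'x* stays. At REST's own covariate means and proportions, least squares returns the raw REST mean. If the two menopause classes are weighted equally, it moves to a 50:50 mix, which need not be AIM's. It would move to AIM's mix only if x* were AIM's values, which the plan does not supply. The same holds for counts if covariate-by-week terms are added.

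**4. Numerical illustration.** Invented complete data: 24 women, 16 postmenopausal, weeks 0-9, with the weekly trend made to depend on age and menopause status. The AIM-like values are assumed (mean age 2 years higher, 40% postmenopausal).

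| Estimate at week 8 | REST margins | Equal class weights | Assumed AIM-like values |
|---|---|---|---|
| Counts, additive covariates (raw change -1.777) | -1.777 | -1.777 | -1.777 |
| Counts, covariate-by-week terms | -1.777 | -1.789 | -2.535 |
| Regression of week-8 percent change (raw -17.92%) | -17.92% | -18.07% | -25.21% |

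The linear slope was -0.1771 per week with and without covariates. Deleting the later weeks for three women gave -1.743 unadjusted and -1.740 adjusted, so the exact equality needs complete data.

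**5. What is left uncorrected.** For one two-level covariate, the shift is its effect on change times the difference in mix. The documents give neither factor. As a yardstick, 10% of the sizing difference is 0.1 x 1.74 = 0.174 per day. That would need, for example, an effect of 1 per day with a 17-point difference in mix, or 0.5 per day with 35 points. These are illustrations, not estimates.

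**6. Does a better method remove it?** Simulation with no pad effect (20,000 runs): 24 REST women, 40 AIM controls (assumed), 80% versus 65% postmenopausal, effect 1 per day, SD 2.85. The expected shift is 1 x 0.15 = 0.15.
- Unadjusted difference: 0.14.
- REST change model evaluated at AIM's mix: -0.01.
- Pooled model with a study-group term: -0.01.

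**The case against.** The strongest reply is that the plan is silent rather than wrong. It never says how the AIM comparison is fitted. AIM is the team's own study, and asking whether pad users changed differently over time fits a pooled group-by-time model. Main effects only is likewise an inference, since the plan calls change its outcome of interest and wants covariates associated with the outcomes. This stands as a limit on the claim: the pad-users-only additive model is the natural reading, not a stated one. It does not remove the problem, because the text as written contains nothing that would carry AIM's case mix into the estimate.

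A reader might infer that the adjustment does nothing on any scale. The documents do not support that. Percent change is an explicit outcome, and there the result depends on reference values that the plan does not state, as the table shows. The fault is that the movement is not toward AIM.

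A reader might also infer that covariates without a significant association will be dropped. The plan says they will be examined for significance, but not that the rest leave the model, so no retention rate can be attached to it.

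Two further points stand. Percent change scales each woman by her baseline, which partly addresses differences in baseline frequency. And this is a pilot seeking preliminary evidence: the 0.174 yardstick is about one-seventh of the 1.20 per day half-width (0.174 / 1.20 = 0.145). Even so, the plan asks whether change differs significantly from AIM, and that result needs a correct label.

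**Conclusion.** The concern holds in this form: the described least squares mean does not adjust the pad-versus-AIM difference for differences between the two samples, although the plan presents it as doing so. For weekly counts this is exact, given an additive model of the pad users and complete data. For percent change, or with covariate-by-week terms, the result is either the raw REST mean or one at an arbitrary weighting, unless AIM values are supplied. If a pooled model is intended, the plan must say so.

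The size of any bias is unknown, because no AIM covariate mix and no covariate effects are given. It would be too strong to infer that the AIM comparison is materially biased. The within-group t-test, the sample size and the 2.1 detectable decline are not touched. The change should be made before analysis, but it is not a flaw in the core pilot design.

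**What to change.** Replace the least squares mean clause with wording such as:

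> The comparison with AIM will use one model on pooled REST and AIM-control women, regressing change from baseline to week 8 on study group, baseline daily hot-flash frequency, age and menopause status. Covariates are fixed in advance. The adjusted group difference will be reported with its 95% confidence interval.

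Week 8 is the AIM time point quoted in the Analytical Plan. Use the same model for percent change and, with baseline PSQI, for the PSQI. Apply it to daytime and nighttime counts, and add the SSAS, only where AIM collected them.

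If only AIM summaries are available, fit the REST change model, evaluate it at AIM's covariate means and proportions, and carry AIM's sampling error into the interval. If neither is available, delete the words adjusted and accurate and report the comparison as unadjusted.

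**Cost.** About three covariate degrees of freedom and a wider interval. With SD 2.85:
- AIM treated as fixed: t(0.975, 23) x 2.85 / sqrt(24) = 2.069 x 0.582 = 1.20 per day.
- Pooled, m AIM controls: t(0.975, 19 + m) x 2.85 x sqrt(1/24 + 1/m) = 1.75 (m = 20), 1.47 (m = 40), 1.32 (m = 80). AIM's control n is not given, so m is assumed.
- Summary version: the REST standard error rises by sqrt(1 + 24s²/23), that is 3% to 12%, if AIM lies an assumed s = 0.25 to 0.5 SD from REST on one covariate.

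The first two options depend on AIM data whose availability the documents do not confirm. None of them removes unmeasured differences between the cohorts.
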